Feasibility Study of 2MRx-CP Use by Patients with Chronic Pain

Phase II: Protocol & Statistical Analysis Plan

Prepared by [name] Research Group:
[name], [name], [name], [name], [name], & [name]

University of Washington
Department of Family Medicine

September 23, 2024
NCT#: NCT06000007

Table of Contents

Feasibility Study of 2MRx-CP Use by Patients with Chronic Pain	3
Feasibility Study of 2MRx-CP Use by Patients with Chronic Pain: University of Washington	
Final Report	3
Study's Overview	3
Background	3
Aims	3
Methods	5
References	8
Appendixes	9
Appendix 1. Outcome measures	9
Eligibility Survey	9
Baseline Survey (T0)	12
1-Month, 3-Month and 6-Month Follow-up Survey	17
Health Care Resource Utilization (HCRU) Survey	22
mHealth App Usability Questionnaire.....	23

Feasibility Study of 2MRx-CP Use by Patients with Chronic Pain: University of Washington Final Report

Study's Overview

Background

Feasibility studies are preliminary studies designed to evaluate the methods and procedures for use in randomized control trials (1-3). These studies aim to identify necessary adjustments that could increase the likelihood of success of larger-scale research (i.e., a well powered efficacy trial) (4). Recently published guidelines emerged to assist researchers on the planning and evaluation of feasibility studies and prevent common misuses (3), which were not available when the original proposal was approved by NIH's NCCIH.

The feasibility randomized control trial (RCT) aimed to test the 2MRx-CP app (i.e., 2Morrow Inc.'s Salty app), a behavioral health app targeted at delivering Acceptance and Commitment Therapy and Cognitive Behavioral Therapy strategies and activities to improve patient function and quality of life. A two-arm feasibility RCT study was conducted with adult patients recruited from primary care settings in rural and urban areas and active self-reported experience of chronic pain. The study aims have been refined and enhanced to align with the latest published guidelines for feasibility trials, while still addressing the original objectives.

Aims

Aim 1. To assess acceptability, appropriateness and feasibility of 2MRx-CP digital therapeutic as an intervention for primary care patients with chronic pain.

App Measure Selection: The preliminary usability and acceptance of the Salty app was measured to ensure alignment with the latest guidelines for feasibility trials while still addressing the core objective of evaluating the intervention for primary care patients with chronic pain. As part of this measurement selection, the mHealth App Usability Questionnaire (MAUQ) was used to measure preliminary usability, replacing the originally proposed Weiner and colleagues (2017, <https://implementationscience.biomedcentral.com/articles/10.1186/s13012-017-0635-3>) usability measure, due to its strong psychometric evidence and better alignment with construct definitions of evaluating a mobile app. Namely, the MAUQ provided a more robust evaluation of app usability, compared to the originally proposed measure. The MAUQ, the SaltyChP (i.e., a custom built measure developed by 2Morrow Inc. to help evaluate usability for product development and support marketability), and descriptives of app usage (i.e., total number of intervention arm patients that successfully engaged use of the app; days the app was used / proportion of days used that were possible; and, total number of badges earned out of the four that were possible) were used to evaluate preliminary usability and acceptance.

Aim 2. To assess feasibility of recruitment, study uptake, and completion of study assessments.

Feasibility Measure Selection: In alignment with standard measures used in feasibility randomized controlled trials, the following feasibility indicators were selected to assess recruitment procedures, retention, outcome measures' adequacy, and feasibility of implementing the intervention (i.e., Salty app):

1. Recruitment procedures: Ability to recruit a diverse sample of participants with various chronic pain diagnoses and exploring the reasons for ineligibility or study decline.
2. Retention: Will participants stay engaged in the study? Survey completion rates by arm and timepoint.
3. Outcomes measures adequacy: a) Are the measures acceptable, appropriate and relevant to the target population? b) Is there evidence of reliability and validity (including responsiveness to change) of measures in the target population?
4. Intervention implementation: a) Was the intervention delivered as intended? b) Were participants engaged with the program components?

Aim 3. To estimate the likely treatment efficacy effect size for a large RCT.

Measures for Preliminary Response to Intervention: Recently published guidelines discourage estimating effect sizes in feasibility studies due to small sample sizes and unrepresentative samples (3). This can lead to inaccurate estimates of parameters and their standard errors, resulting in misleading power calculations (3, 5). Instead, these guidelines recommend focusing on confidence intervals rather than point estimates of effect size (3). Aim 3 has been expanded to include exploring preliminary responses to the intervention and generating initial parameter estimates for sample size calculations. This refinement builds upon Aim 3 by incorporating additional aspects aligned with current best practices for feasibility studies. Initial parameter estimates for a sample size calculation were calculated to detect clinically meaningful differences with adequate power. Outcome measures included a pain interference measure (PROMIS Pain Interference Short Form 6b), depression symptoms (PHQ-9), anxiety symptoms (GAD-7), and a pain intensity rating.

Methods

Study Design

This study used a 2-arm, open, feasibility RCT with parallel design. We assessed participants at four timepoints, at baseline (T0), 1 month (T1), 3 months (T2) and 6 months (T3) post intervention.

Inclusion and Exclusion Criteria

Eligibility criteria included: 1) adult patients (i.e., aged ≥ 18 years) with chronic non-cancer related pain (i.e., pain experience was current and present for ≥ 3 months), 2) documentation of at least one International Classification of Diseases (ICD) code of a common pain related conditions (e.g., low back pain, musculoskeletal pain, fibromyalgia) based on published identified chronic pain conditions (6), 3) had at least two primary care visits within the last 12 months at the time of recruitment, 4) significant levels of self-reported pain interference (i.e., PROMIS Pain Interference Short Form 6b T-score of 55 or above), 5) daily smartphone access, 5) ability to download an app, 6) willingness to engage in a 3-month chronic pain self-management program administered via an app, 7) speak English, and 8) consent to randomization in the study.

Participants were excluded if: 1) their pain was related to cancer, 2) they had plans for surgery within the next 3 months, 3) they were pregnant, or 4) they were receiving hospice services.

Recruitment and Screening

Potential participants were identified using electronic health record (EHR) data extracted from three health systems, which included information from 60 primary care clinics in Washington and Idaho. These data were accessed through the Data QUEST Coordinating Center's EHR data repositories. From the generated potential participant lists, random cohorts were created for recruitment email blasts.

Patients were invited to participate via direct email. Each email contained a link to an interest survey with three options: 1) proceed to the study eligibility survey, 2) request a call back from a study coordinator for further discussion, or 3) opt out of the study. Patients who proceeded to the eligibility survey were informed at the end of the survey of their study eligibility. Those who were eligible were directed to an e-consent form. The e-consent form required patients to either 1) confirm that they wanted to participate in the study, 2) request a call to discuss the study with a study coordinator first, or 3) confirm that they were not interested in participating in the study. Patients who confirmed their interest in participating in the study were asked to sign the e-consent form. A study coordinator would then counter-sign the e-consent form. A study coordinator would follow up with any call requests and if needed assist with the consent over the phone.

Group Allocation

Participants were randomized using a stratified method based on healthcare system and age, aiming to distribute them equally across health systems while matching the national age distribution of individuals living with chronic pain. This stratified allocation was implemented in the REDCap randomization module. The intervention group received access to the 2Morrow Inc. digital behavioral health Salty app (2MRx-CP), while the control group received treatment as usual.

Upon randomization, the REDCap project was programmed to send automatic emails to participants with links to their baseline survey. Participants in both arms needed to complete the baseline survey within two weeks to be considered fully enrolled in the study. Participants in the intervention arm were emailed separate instructions about how to download and access the app and create a user profile. These participants were reminded up to three times (including two automatic email reminders and one phone call from a study coordinator) in the two-week enrollment window. Those that completed the baseline survey, but did not access the app, are included in the study. Participants in the intervention arm that encountered technical difficulties with the app were connected with the tech team at 2Morrow, Inc.

Intervention: The Salty Program, 2Morrow, Inc.

Data collection

Data was collected at baseline (T0), 1-month (T1), 3-month follow (T2), and at 6-month follow up (T3) via REDCap which is a secure, HIPAA-compliant web-based application used for data capture and management. Automatic survey invitation emails were programmed in REDCap to be emailed to participants at each study time point. In these automatic emails, participants were asked to complete surveys via a personalized REDCap survey link. They had two weeks to complete each survey. During the two-week data collection window, follow-up for participants who had not yet completed their surveys could include automatic REDCap email reminders (up to two) and a reminder call and/or email from the study team. Participants could return to their surveys using their personalized survey link at any time during the data collection window. Time spent completing surveys was not recorded. The surveys utilized REDCap enhanced radios and checkboxes for a better user experience across different devices (laptops, tablets, and mobile phones). Participants received a \$50 e-gift card for each survey they completed, up to \$200 total for the entire study. REDCap survey settings allowed participants to skip some questions. In accordance with IRB requirements, participants were not obligated to answer any questions they felt uncomfortable with; as a result, the REDCap survey was configured to allow optional responses. For the purposes of statistical analysis, only complete data sets were included for each outcome measure. Specifically, if a participant omitted any subscale items necessary to calculate a total score, their data were excluded from the summary statistics and analyses for that measure.

The data were extracted from REDCap at the completion of the study for data analyses. No identifiers were maintained, and data were stored using a password protected delimited file and stored in an access-controlled location on a secure HIPAA-compliant server at UW. 2Morrow gave UW usability data logged by their platform. UW linked the 2Morrow usability data to de-identified study identifiers, links to identifiers were then destroyed, and stored similarly to the REDCap derived data.

Outcome measures

(Appendix 1 includes a copy of all outcome measures)

Intervention and Control Group

1. Baseline survey, administered at T0, consisted of demographic questions (education, employment, marital status, income and insurance), social determinants of health questions (living situation, electricity, food, transportation), and the following tools:

- **Patient-Reported Outcomes Measurement Information System (PROMIS) Pain Interference Scale – Short Form 6b** is a six-item self-report questionnaire that assesses the impact of pain on various aspects of a person's life (e.g., social, cognitive, emotional, physical and recreational activities) over the last 7 days (7). Responses are scored using a 5-point ordinal rating scale from 1 to 5 (1=Not at all, 2=A little bit, 3=Somewhat, 4=Quite a bit, 5=Very much). Raw score totals are converted to T-score using the scoring manual (8). T-score of 50 is the mean for the U.S. general population with a standard deviation of 10; the higher the T-score, the worse the pain interference.
 - **Patient Health Questionnaire – 9 (PHQ-9)** is a 10-item self-report questionnaire used to assess depression symptoms consistent with criteria for Major Depressive Disorder over the last two weeks (9). The tool uses a 4-point rating scale (0=not at all, 1=several days, 2=more than half the days, 3=nearly every day) and has demonstrated strong psychometric properties including high levels of specificity and sensitivity of major depressive disorders (9, 10).
 - **Generalized Anxiety Disorder 7-item scale (GAD-7)** is a widely used self-reported questionnaire to measure the severity of generalized anxiety disorder symptoms over the past two weeks (11). Responses are scored from 0 to 3 (0= Not at all, 1= Several days, 2= More than half days, 4= Nearly every day). The tool has shown strong psychometric properties, including high evidence of internal consistency and reliability (12).
 - An additional set of 4 questions explored participants' recent primary care visits, engagement with the Salty app, and receipt of treatment for their pain in the last month.
2. Follow-up survey, administered at T1, T2, and T3, consisted of the following tools: PROMIS pain interference, PHQ-9, and GAD-7, and pain intensity.
 3. **The Health Care Utilization (HCRU)** (Administered at T2 and T3).

Intervention Group

1. **mHealth App Usability Questionnaire (MAUQ)**, administered at T2, is a 21-item survey that assesses mobile health (mHealth) app usability across three domains: ease of use and satisfaction (8 items), system information arrangement (6 items), and usefulness (7 items). It uses a 7-point Likert-type scale (1=strongly disagree to 7=strongly agree) and has established reliability and validity evidence (13).
2. **Salty Program for Chronic Pain Questionnaire (SaltyChP)** is a 6-item survey developed by 2Morrow, Inc., that explores specific aspects of the app (e.g., patients' satisfaction with various specific app features, patient ratings of helpfulness of the app for pain, likelihood to recommend the app to others) using Likert-type response scales. The survey includes two open-ended questions addressing what was helpful and what could be improved in the app. This survey was administered at both T2 and T3.

References

1. National Center for Complementary and Integrative Health. Pilot Studies: Common Uses and Misuses [Available from: <https://www.nccih.nih.gov/grants/pilot-studies-common-uses-and-misuses>].
8. Health NIO. PAIN INTERFERENCE A brief guide to the PROMIS Pain Interference instruments. 2018.

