Appendix 1. Outcome measures

Eligibility Survey

What is your age?	 Younger than 18 years old  18-29  30-44  45-64  65 or older
What is your assigned sex at birth?	 Male  Female  Intersex
Which gender do you identify most with?	 Men  Women  Non-binary  Prefer to self-describe  Prefer not to answer
Please describe: -----	
Which of the following best describes you?	 American Indian or Alaskan Native  Asian American  Black or African American  Middle Eastern and/or North African decent  Native Hawaiian or Other Pacific Islander  White  Two or more races  Other  Prefer not to answer
Please specify: -----	
Are you of Hispanic or Latinx origin?	 Yes  No
How long have you been experiencing pain?	 Less than 3 months  3 months to 1 year  1 year-3 years  3 or more years

In the past 7 days, how much did pain interfere with...	Not at all	A little bit	Somewhat	Quite a bit	Very much
your enjoyment of life?					
your ability to concentrate?					
your day-to-day activities?					
your enjoyment of recreational activities?					
doing your tasks away from home (e.g., getting groceries, running errands)?					
How often did pain keep you from socializing with others?	 Never	 Rarely	 Sometimes	 Often	 Always

☐ 41.6

☐ 49.6

☐ 52.0

☐ 53.9

☐ 55.6

☐ 57.1

☐ 58.5

☐ 59.9

☐ 61.2

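### The only T-score list in the Eligibility Survey has 17 values, which cannot be a complete conversion for the six-item Short Form 6b (25 raw totals) named in the entry criterion

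*Combined protocol and SAP*

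**What the plan says.** Methods, Inclusion and Exclusion Criteria, requires a "PROMIS Pain Interference Short Form 6b T-score of 55 or above". Under Outcome measures, the instrument "is a six-item self-report questionnaire that assesses the impact of pain on various aspects of a person's life", and "Responses are scored using a 5-point ordinal rating scale from 1 to 5". That section refers the conversion of raw totals to the cited scoring manual (reference 8) and reproduces no table.

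The Eligibility Survey in Appendix 1 prints five items on what pain interfered with and a sixth, "How often did pain keep you from socializing with others". Directly after them stands a list of T-scores from 41.6 to 75.6, with no label, raw-score key or scoring rule. It is the only T-score list in the document. The Baseline and Follow-up surveys repeat the six items without it.

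On how the decision reached patients, Recruitment and Screening says: "Patients who proceeded to the eligibility survey were informed at the end of the survey of their study eligibility".

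**The concern.** A conversion table must give one T-score for each possible raw total. The list printed after the six items has too few values for six items, yet it is the only conversion visible in the survey that told patients whether they were eligible.

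The other entry criteria cover pain duration, a diagnosis code, recent primary care visits, phone access and the like. Only this one sets a level of severity. If the wrong table was behind it, the study's description of whom it enrolled is inaccurate. Aim 2 would then report eligibility and reasons for ineligibility against a criterion that was not the one applied. Aim 3 would take its starting values for the next trial's sample size from a population other than the one described. The faulty screen could also be carried forward into that trial.

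**Working it through.** **Inputs from the documents**
- Number of items: 6 (Outcome measures; the Eligibility Survey prints 6).
- Response levels per item: 5, scored 1 to 5 (Outcome measures).
- Entry cut: T-score of at least 55 (Inclusion and Exclusion Criteria).
- Listed T-scores (Eligibility Survey): 41.6, 49.6, 52.0, 53.9, 55.6, 57.1, 58.5, 59.9, 61.2, 62.5, 63.8, 65.2, 66.6, 68.0, 69.7, 71.6, 75.6. That is 17 values, all distinct.

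**Step 1: how many totals the stated form has.** With k items of m levels, the number of raw totals is k(m − 1) + 1. For k = 6 and m = 5 this is 6 × 4 + 1 = 25 (totals 6 to 30). The list is 25 − 17 = 8 short.

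**Step 2: which form has 17 totals.** With five levels, the count is 4k + 1:
- 3 items: 13
- 4 items: 17
- 5 items: 21
- 6 items: 25
- 7 items: 29

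Only four items give 17 (totals 4 to 20). Holding six items and varying the levels from 2 to 7 gives 7, 13, 19, 25, 31 and 37, never 17.

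**Step 3: could eight rows have dropped out of the text?** Successive differences are 8.0, 2.4, 1.9, 1.7, 1.5, 1.4, 1.4, 1.3, 1.3, 1.3, 1.4, 1.4, 1.4, 1.7, 1.9, 4.0. They narrow smoothly to the middle and widen smoothly towards both ends. No interior step stands out as a place where rows are missing. Loss is unlikely, though it cannot be ruled out from the text alone.

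**Step 4: what the cut would mean if this list were used.** The first value at or above 55 is the fifth, 55.6. The scoring logic is not shown, so these are illustrations and not findings:
- Four items scored on a matching four-item table: the cut is raw 4 + 4 = 8 out of 20, a mean item score of 8/4 = 2.0. Two of the six printed items are not used.
- Six-item total looked up by raw value on a 4-to-20 table: raw 6 gives 52.0, raw 7 gives 53.9 and raw 8 gives 55.6, so the cut is 8 out of 30. Totals 21 to 30 (10 of 25) have no T-score.
- Six-item total aligned from its minimum: raw 6 gives 41.6 and raw 10 gives 55.6, so the cut is 10 out of 30. Totals 23 to 30 (8 of 25) have no T-score.

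The raw total that meets the cut on the true Short Form 6b table cannot be computed here, because that table is not in the documents. The number and direction of any misclassifications therefore cannot be derived.

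**The case against.** The strongest reply is that the list may not have decided anything. It is unlabelled and carries no raw-score key, branching rule or eligibility flag. It could be the live scoring field, a display field or a leftover. The only statement about conversion points to the scoring manual, which is compatible with correct scoring. This stands. A reader might infer that patients were in fact admitted on the wrong table, but the documents do not say so. They show only that no other conversion appears in the survey that determined eligibility.

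Second, even if the list was used, the exact match to four items may mean that four items were scored on their own proper table. If that T-score is on the same metric as Short Form 6b (an assumption the documents neither confirm nor deny), the cut would still be a T-score of at least 55, measured with fewer items. The population might then differ little. This also stands as the mild end of the range. It would still not be the criterion as written.

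Third, a reader might infer that the pain interference outcome is mis-scaled throughout. The Baseline and Follow-up surveys contain no such list, so this is unsupported and remains only a question to put to the sponsor.

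None of this explains why 17 values follow six items.

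**Conclusion.** The mismatch holds: 17 listed T-scores against the 25 that a six-item form scored 1 to 5 requires. It rests on the documents' own item count and scoring, and on the list being intact, which its smooth steps support.

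The consequence is conditional. If this field drove the entry decision, the cut was not the stated Short Form 6b criterion. Whether it did is not shown, the effect on who was enrolled cannot be sized from the documents, and use of the list at T0 to T3 is not shown. Confidence is high in the discrepancy and low in how much harm it did. It still needs an answer, because it concerns the only severity threshold for entry.

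**What to change.** 1. State which conversion was programmed at screening and which was used at T0, T1, T2 and T3.
2. Reconcile the Inclusion and Exclusion Criteria, the Outcome measures section and the Eligibility Survey. Replace the 17-value field with the 25-row Short Form 6b conversion from the cited manual.
3. Recompute the screening T-scores from the stored item responses. Recompute T0 to T3 only if the same 17-value list was used there.
4. Report how many screened patients change eligibility status and how many randomised patients have a recomputed T-score below 55.
5. Remove no randomised patient from the main analysis because of re-scoring. If any fall below 55, repeat Aims 2 and 3 without them as a sensitivity analysis.

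The cost is a re-scoring script and a short table. This assumes that item-level screening responses were kept, including those of people found ineligible, which the documents do not state. If they were not kept for that group, the change in status can be reported only for those retained, and the report should say so. If the programmed scoring proves to have been Short Form 6b all along, the re-scoring will simply confirm it, and a sentence plus the corrected appendix closes the matter.

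### Full enrolment depends on returning a baseline survey sent after open randomisation, so loss before T0 can drop out of the retention rates and the arm comparison

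*Combined protocol and SAP*

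**What the plan says.** The order of events is set out under Methods, Group Allocation. Randomisation comes first: "Upon randomization, the REDCap project was programmed to send automatic emails to participants with links to their baseline survey". Enrolment then depends on that survey: "Participants in both arms needed to complete the baseline survey within two weeks to be considered fully enrolled in the study". One sentence says who is kept: "Those that completed the baseline survey, but did not access the app, are included in the study". No sentence does the same for randomised participants who did not return T0.

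Under Study Design the trial is described as open: "This study used a 2-arm, open, feasibility RCT with parallel design". Group Allocation adds a task for one arm only: "Participants in the intervention arm were emailed separate instructions about how to download and access the app and create a user profile".

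Under Aims, Aim 2, the retention measure is "Survey completion rates by arm and timepoint", with no denominator. The same aim covers study uptake. Aim 1 counts intervention patients who used the app, and Aim 3 compares arms to obtain parameters for a larger trial. Data collection adds a complete-data rule for each outcome measure. No intention-to-treat rule or other analysis set appears anywhere.

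**The concern.** Membership of the study is tied to something participants do after allocation, in a trial without masking. A person who is randomised and then disengages within two weeks is an early dropout. Under this rule that person can instead be treated as never having joined.

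This matters more here than in most trials, because uptake and completion of assessments are results the study exists to produce. An attrition allowance for a later trial, taken from rates among the fully enrolled, would leave out the first loss after randomisation. App uptake under Aim 1 is affected in the same way if people assigned to the app who miss T0 leave its denominator. For Aim 3, a selection step after allocation means the two groups compared are no longer the two groups that were randomised.

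**Working it through.** The documents state no sample size, dropout rate or retention target, so there is no planned figure to reproduce. What can be checked is the order of events and what follows from it. Every value of b, r and d below is an assumption.

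**1. Who is in the study.** Randomise; send the T0 survey; allow two weeks; count as fully enrolled only those who returned it. The one inclusion sentence rescues T0 returners who never opened the app. Departure from the randomised groups therefore concerns T0 non-returners only.

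**2. Retention.** Let b be the share of randomised participants who return T0, and r the follow-up completion among the fully enrolled. If non-returners contribute no later surveys, retention among all randomised is b × r. The enrolled-only rate is r, which is too high by r(1 − b), a factor of 1/b. With r = 0.80:

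| b | all randomised, b × r | overstatement, r(1 − b) | factor 1/b |
|---|---|---|---|
| 0.95 | 76% | 4 points | 1.05 |
| 0.90 | 72% | 8 points | 1.11 |
| 0.85 | 68% | 12 points | 1.18 |
| 0.80 | 64% | 16 points | 1.25 |

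On these terms the enrolled-only rate is never too low, and it is right only if b = 1.

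**3. A hidden difference between arms.** Take r = 0.85 in both arms, with T0 return of 0.80 (intervention) and 0.95 (control).

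- Enrolled-only gap: 85% − 85% = 0 points.
- All-randomised gap: 0.95 × 0.85 − 0.80 × 0.85 = 80.75% − 68% = 12.75 points.

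**4. Aim 3.** Let d be the mean outcome of T0 non-returners minus that of returners within an arm (1 = intervention, 0 = control). Leaving non-returners out shifts the intervention-minus-control difference by (1 − b0)d0 − (1 − b1)d1. In PROMIS T-score points:

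- b1 = 0.80, b0 = 0.95, d = 5 in both arms: 0.05 × 5 − 0.20 × 5 = −0.75.
- Same return, d = 10 in both arms: 0.05 × 10 − 0.20 × 10 = −1.5.
- b1 = 0.95, b0 = 0.85, d = 5 in both arms: 0.15 × 5 − 0.05 × 5 = +0.5.
- b1 = b0 = 0.80, d1 = 5, d0 = 0: 0 − 0.20 × 5 = −1.0.
- b1 = b0 = 0.90, d = 5 in both arms: 0.10 × 5 − 0.10 × 5 = 0.

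The bias can take either sign. It is zero when loss is equal and equally selective in the two arms, or unrelated to outcome.

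**5. Data available before randomisation.** Eligibility requires a PROMIS pain interference T-score of at least 55, so a screening score should exist for everyone randomised. The Eligibility Survey in Appendix 1 also asks for average pain intensity and demographics. It contains neither the PHQ-9 nor the GAD-7.

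**The case against.** The strongest reply is that the plan never says T0 non-returners are dropped from any table. Being fully enrolled is a status, and the only analysis exclusion actually stated is for missing items within a measure. T0 is one of the four timepoints, so rates by arm and timepoint would show the early loss if all randomised participants were the denominator. Study uptake is listed separately in Aim 2 and could carry it too. This stands to the extent that exclusion is implied and not explicit, and retention is overstated only if the fully enrolled are the denominator. It does not remove the problem: the one rule given points to the enrolled group, and nothing points to the randomised group.

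A reader might infer that the intervention arm received extra survey reminders, since the text following the app instructions says "These participants were reminded up to three times" and places this in the enrolment window. The documents do not establish that. Data collection describes up to two automatic emails and a call or email from the team with no split by arm, and these may be the same contacts. Only the app instructions are clearly specific to one arm.

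A reader might also infer that the arms are not comparable. That too goes beyond the text, since the bias may be zero. It may also be small beside the precision of a feasibility trial: at an assumed 50 to 100 per arm, the 95% half-width for a difference is 1.96 × √(2/n), or 0.39 to 0.28 SD. On the reference SD of 10 given under Outcome measures, the non-zero shifts above are 0.05 to 0.15 SD. The plan itself cautions against point effect sizes. This limits the Aim 3 part of the point and leaves the retention part untouched.

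**Conclusion.** The point holds in conditional form. The stated enrolment rule makes the study population depend on behaviour after open allocation, and no text restores the randomised denominator. If the rule is followed in the tables, the overstatement of retention is r(1 − b): 8 to 16 points for 10% to 20% loss before T0 with 80% follow-up among the enrolled. Those inputs are assumed, because the documents give no counts.

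For Aim 3 the supportable statement is that randomisation no longer protects the comparison. Neither the presence nor the direction of bias can be read from the documents.

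**What to change.** - Define the analysis population as everyone randomised, in the assigned arm.
- Use all randomised as the denominator for T0, T1, T2 and T3 completion, by arm, and all randomised to the intervention arm for app uptake, with exact 95% confidence intervals.
- Show loss between randomisation and T0 as its own line, by arm.
- Compare T0 returners and non-returners on the Eligibility Survey data: PROMIS pain interference, pain intensity and demographics.
- Report rates among the fully enrolled as secondary.
- In Aim 3, keep every randomised participant who has a follow-up score. For PROMIS and pain intensity, use the screening score as the covariate for everyone. Filling it in only where T0 is missing would mix scores selected at 55 or above with unselected ones. For PHQ-9 and GAD-7, which have no screening score, treat a missing T0 value as a missing baseline covariate and do not exclude the person. State that the complete-data rule does not override this.

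No new data collection is needed. Reported retention becomes less favourable, and the Aim 3 covariate changes for two of the four outcomes. If survey invitations stopped after a missed T0, those participants have no later outcomes to recover. They then count as lost in the completion rates, and Aim 3 can only describe them by their screening data.
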